## 4.2 Exclusion Criteria

- Subjects with active CNS metastases are excluded. If CNS metastases are treated and subjects are at neurologic baseline for at least 2 weeks prior to enrollment, they will be eligible but will need a Brain MRI prior to enrollment. Subjects must be off corticosteroids or on a dose of less than 10mg per day.
- Subjects with active, known or suspected autoimmune disease. Subjects with vitiligo, type I diabetes mellitus, residual hypothyroidism due to autoimmune thyroiditis only requiring hormone replacement, or conditions not expected to recur in the absence of an external trigger are permitted to enroll.
- Subjects with a condition requiring systemic treatment with either corticosteroids (>10 mg daily prednisone equivalent) or other immunosuppressive medications within 14 days of enrollment. Inhaled or topical steroids, and adrenal replacement steroid doses > 10 mg daily prednisone equivalent, are permitted in the absence of active autoimmune disease.
- Prior therapy with anti-PD-1, anti-PD-L1, anti-PD-L2, anti-CD137, or anti-CTLA-4 antibody (including ipilimumab or any other antibody or drug specifically targeting T-cell costimulation or checkpoint pathways).
- Prior therapy with ibrutinib or other BTK inhibitors.
- Previous or concurrent cancer within 3 years prior to treatment start EXCEPT for curatively treated cervical cancer in situ, non-melanoma skin cancer, superficial bladder tumors [Ta (non-invasive tumor), Tis (carcinoma in situ) and T1 (tumor invades lamina propria)].
- Known history of human immunodeficiency virus (HIV) infection or acquired immunodeficiency syndrome (AIDS).
- Serologic status reflecting active hepatitis B or C infection. Patients who are hepatitis B core antibody positive and who are antigen negative, will need to have a negative PCR result prior to enrollment. Those who are hepatitis B antigen positive or PCR positive, will be excluded.
- Subjects with Child Pugh B or C cirrhosis.
- History of severe hypersensitivity reactions to other monoclonal antibodies
- Substance abuse, medical, psychological or social conditions that may interfere with the patient's participation in the study or evaluation of the study results.
- History or concurrent condition of interstitial lung disease of any grade or severely impaired pulmonary function.
- Unresolved toxicity higher than CTCAE grade 1 attributed to any prior therapy or procedure, excluding alopecia.

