### 5.1.2 Definition of dose-limiting toxicity

A DLT is defined as any toxicity not attributable to the disease or disease-related processes under investigation, which occurs from the start of combination ( post dose Day 1 Cycle 1) up to 42 days and is considered by the Investigator to be definitely, probably, or possibly related to the treatment. A DLT will be defined as any Grade 3 or higher treatment-related toxicity that occurs during the DLT evaluation period, including:

1. Any Grade 4 immune-related AE (irAE) irrespective of duration
2. Any Grade 3 or 4 non-infectious pneumonitis irrespective of duration
3. Any Grade 3 irAE, excluding colitis or pneumonitis, that does not downgrade to Grade  $\leq 2$  within 3 days after onset despite maximal supportive care including systemic corticosteroids or downgrade to Grade  $\leq 1$  within 14 days after onset of the event.
4. Any  $\geq$  Grade 2 pneumonitis or interstitial lung disease (ILD) that does not resolve to grade 1 within 3 days of the initiation of maximal supportive care
5. Liver transaminase elevation higher than  $10 \times$  upper limit of normal (ULN) or total bilirubin higher than  $5 \times$  ULN **that lasts for longer than 7 days**. Any grade 3-4 non hematologic toxicity which does not resolve within 4 days will be considered a DLT.

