## 6. Visit schedule and Assessments

### 6.1 Screening First Visit

Screening examinations will only be performed after having received the subject's written informed consent.

The following examinations will be performed within 28 days prior to the first treatment:

- Written subject informed consent to be obtained prior to any screening assessments.
- Complete medical history and physical examination, including demographics, surgery, therapies, medications, smoking, alcohol history, co-existing diseases, allergies, NYHA classification, vital signs (heart rate, respiration rate, temperature, and BP), weight and review of systems.
- Medical history ECOG Performance Status Assessment
- 12-lead ECG
- Radiologic assessment: CT scan or MRI (chest, abdomen, pelvis) with tumor measurement by RECIST V1.1 and irRC criteria
- Coagulation (PT-INR and aPTT)
- Hematology (hemoglobin, HCT, RBC, WBC count with differential (neutrophils, bands, lymphocytes, monocytes, eosinophils and basophils) and platelet count
- Chemistry (ALT, AST, alkaline phosphatase, total bilirubin, direct bilirubin, lactate dehydrogenase (LDH), creatine kinase, lipase, amylase, glucose, calcium phosphate, magnesium, bicarbonate, sodium, potassium, chloride, creatinine, blood

- urea nitrogen (BUN), total protein and albumin
- TSH, free T4
- [REDACTED]
- Carcinoembryonic antigen (CEA)
- Serum/urine pregnancy test (if applicable)
- Screening for Hepatitis B and C
- Urinalysis including blood, glucose, protein, specific gravity
- [REDACTED]

## 6.2 Cycle 1 Day 1

- History and assessment to include physical examination, vital signs (heart rate, respiration rate, temperature and BP) and review of systems
- Baseline Toxicity/AE assessment after first dose
- ECOG Performance Status Assessment
- Hematology (hemoglobin, HCT, RBC, WBC with differential (neutrophils, bands, lymphocytes, monocytes, eosinophils and basophils) and platelet count
- Chemistry (ALT, AST, AP, total bilirubin, direct bilirubin, LDH, creatine kinase, lipase, amylase glucose, calcium, phosphate, magnesium, bicarbonate, sodium, potassium, chloride, creatinine, BUN, total protein and albumin

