## 6.6 Calendar

	Screening within 28 days of CID1	Cycle 1 Day 1 ± 2 days	Cycle 2 day 1 ± 2 days and subsequent cycles	Cycle 3 day 1 ± 5 day and every 3 rd cycle thereafter	EOT m	Safety Follow-Up Visit ± 7 days n	Post-Progression Follow-up j

Complete History/Physical a	X				X		
History & Assessment b		X	X			X	
Toxicity Notation		X	X		X	X	
ECOG	X	X	X		X	X	
ECG	X						
Tumor Measurement/Disease Assessment c	X			X	X		
Hematology d	X	X	X		X		
Chemistry e	X	X	X		X		
Coagulation f	X						
Urinalysis g	X						
TSH, free T4	X			X			
CEA	X			X			
Hepatitis Screening h	X						
Serum/urine Pregnancy, if applicable i	X						
Survival f/u j							X
██████████	■						
██████████							
██████████	■			■			
██████████							

- a. Complete medical history and physical examination including demographics, surgery, therapies, medications, smoking, alcohol history, co-existing diseases, allergy, NYHA classification, vital signs (heart rate, respiration rate, temperature and BP), height, weight and review of systems. A full physical exam should be performed during screening.
- b. History and assessment including brief examination, vital signs and review of systems. Note all toxicities and adverse events, using CTCAE version 4.03 and in accordance with section 9.1. The investigator or qualified designee will also perform a directed physical exam as clinically indicated prior to each treatment cycle administration.
- c. Tumor assessment using CT or MRI (chest, abdomen, pelvis) (at investigator's discretion) will be collected at screening, after every 3 cycles, and as clinically indicated. Tumor response will be assessed using RECIST 1.1 and irRC criteria. Tumor measurement/disease assessment should be performed within 7 days at the beginning of every 3rd cycle.
- d. Hemoglobin, hematocrit, red blood cell count, white blood cell count with differential (neutrophils, bands, lymphocytes, monocytes, eosinophils and basophils) and platelet count.
- e. ALT, AST, alkaline phosphatase, total bilirubin, direct bilirubin, LDH, creatine kinase, lipase, amylase, glucose, calcium, phosphate, magnesium, bicarbonate, sodium, potassium, chloride, creatinine, blood urea nitrogen (BUN), total protein and albumin.

- f. PT-INR and aPTT.
- g. Urinalysis including blood, glucose, protein, specific gravity

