## **7. Assessment types**

### **7.1 Pre-Treatment Assessments**

The nature of the study and the associated potential risks will be explained to all study candidates and a signed informed consent must be obtained before any study-specific Pre-Treatment procedures are performed. Pre-Treatment assessments must be completed and reviewed within 28 days prior to the start of study drug treatment to ensure eligibility for study entry

Pre-Treatment evaluations will include inclusion/exclusion criteria evaluation, demographic data collection, ECOG performance status, NYHA classification, medical and surgical history collection, vital signs, complete physical examination (including height and weight), 12-lead ECG, biochemistry, hematology and urinalysis, pregnancy test (urine or serum  $\beta$ - hCG in women of childbearing potential only), and tumor assessments

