## **8. Safety monitoring and reporting**

### **8.1 Adverse Events**

#### **8.1.1 Definitions**

An Adverse event (AE) is any unfavorable and unintended sign, symptom, or disease temporally associated with the use of an investigational medicinal product (IMP) or other protocol-imposed intervention, regardless of attribution. Medical conditions/diseases present before starting study drug are only considered adverse events if they worsen after starting study drug. Abnormal laboratory values or test results constitute adverse events only if they induce clinical signs or symptoms, are considered clinically significant, or require therapy. Clinically significant laboratory results are those requiring a change in the patient's treatment, further diagnostic testing or specific clinical intervention (i.e., treatment delays or dose modifications, etc). The occurrence of adverse events should be sought by non-directive questioning of the patient at each visit during the study. Adverse events also may be detected when they are volunteered by the patient during or between visits or through physical examination, laboratory test, or other assessments. As far as possible, each adverse event should be evaluated by the investigator to determine:

- the severity grade (mild, moderate, severe) or (grade 1-4)
- its relationship to either or the study drugs (unrelated, unlikely, possible, probable, definite)
- its duration (start and end dates or if continuing at final exam)
- action taken (no action taken; study drug dosage adjusted/temporarily interrupted; study drug permanently discontinued due to this adverse event; concomitant medication taken; non-drug therapy given; hospitalization/prolonged hospitalization)
- whether it constitutes a serious adverse event (SAE)

Attribution is the relationship between an adverse event or serious adverse event and the study treatment. Attribution will be assigned as follows:

- Definite: The AE is clearly related to the study treatment;
- Probable: The AE is likely related to the study treatment;
- Possible: The AE may be related to the study treatment;
- Unlikely: The AE is doubtfully related to the study treatment;
- Unrelated: The AE is clearly not related to the study treatment.

A serious adverse event is an undesirable sign, symptom or medical condition which:

1. Is fatal or life-threatening.
2. Requires or prolongs hospitalization.
3. Results in persistent or significant disability/incapacity.

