### **Safety**

Safety data will not be formally analyzed. All subjects who receive at least one dose of ibrutinib or pembrolizumab will be included in the assessment of the safety profile (safety analysis set). At the end of the study, appropriate summaries of all safety data will be produced, as defined below.

Data from all cycles of initial treatment will be combined in the presentation of safety data. AEs will be listed individually by subject and dose group/expansion phase arm. For subjects who have a dose modification, all AEs (due to drug or otherwise) will be assigned to the initial dose group. The number of subjects experiencing each AE will be summarized by the Medical Dictionary for Regulatory Activities (MedDRA) system organ class, MedDRA preferred term and CTCAE grade. The number and percentage of subjects with adverse events in different categories (e.g., causally related, CTCAE grade  $\geq 3$  etc.) will be summarized by dose group/expansion phase arm, and events in each category will be further summarized by MedDRA system organ class and preferred term, by dose group. SAEs will be summarized separately if a sufficient number occur.

Any AE occurring before the first dose of investigational product (i.e., before study Day 1) will be included in the data listings but will not be included in the summary tables of adverse events.

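### The toxicity assessment labelled as baseline is timed after the first dose and no pre-dose one is explicitly scheduled, so low-grade symptoms and Day 1 reactions can be misassigned in the adverse event tables

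*Combined protocol and SAP*

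**What the plan says.** Section 6.2 (Cycle 1 Day 1) includes a "Baseline Toxicity/AE assessment after first dose". From Cycle 2 onward, section 6.3 lists a toxicity/AE assessment without the word baseline.

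Before dosing, section 6.1 introduces its list with "The following examinations will be performed within 28 days prior to the first treatment". That list contains history, physical examination, review of systems, ECG, imaging and laboratory tests, but no toxicity item. Section 7.1 begins its list with "Pre-Treatment evaluations will include inclusion/exclusion criteria evaluation, demographic data collection, ECOG performance status" and names no toxicity assessment either. In the calendar (6.6), the row "Toxicity Notation" is blank at screening and first marked at Cycle 1 Day 1. Footnote b, attached to the History & Assessment row that is also first marked that day, asks for toxicities to be noted by CTCAE version 4.03. It does not place this noting before or after the dose.

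Four other provisions rely on the state before treatment or on the time of first dose:

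- Section 8.1.1: "Medical conditions/diseases present before starting study drug are only considered adverse events if they worsen after starting study drug".
- Section 4.2 excludes patients with "Unresolved toxicity higher than CTCAE grade 1 attributed to any prior therapy or procedure, excluding alopecia".
- Section 5.1.2 defines a DLT as a toxicity "which occurs from the start of combination ( post dose Day 1 Cycle 1) up to 42 days".
- Section 9.7, Safety: "Any AE occurring before the first dose of investigational product (i.e., before study Day 1) will be included in the data listings", with such events kept out of the summary tables.

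Section 9.4.2 plans summaries of treatment-emergent and drug-related events by worst grade. Neither 9.4.2 nor 9.7 defines treatment-emergent.

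**The concern.** A baseline grade is the reference against which later grades are judged. If site staff follow section 6.2 literally, the record carrying that label is made when the patient has already received study drug. Two errors become possible.

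- A reaction already present at the post-dose check may be filed as baseline, so that the same grade later does not look like a worsening.
- A mild symptom that the patient brought into the study may have no grade from just before dosing. It may then first appear in the on-treatment record and be tabulated as treatment-emergent or drug-related.

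Safety and tolerability are the primary objective of phase I, and the trial has no control arm against which background symptoms could be judged. A symptom grade not recorded before the first dose cannot be recovered later.

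**Working it through.** No arithmetic applies: the point concerns the timing of an assessment, and the plan attaches no figure to it. The check is to set the provisions side by side.

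**1. Is any toxicity assessment placed before the first dose?** By named item, no: 6.1, 7.1 and the screening cell of the calendar row have none. The only text that times the Day 1 toxicity assessment relative to dosing is in 6.2, and it says after. Footnote b is silent on order. It does require a directed examination, as clinically indicated, ahead of each cycle's administration, so a pre-dose reading of the CTCAE noting is possible but not stated.

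**2. Does the label in 6.2 fit the rules that use a baseline?**

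| Provision | Reference point | Fit with a baseline taken after dosing |
|---|---|---|
| 8.1.1, pre-existing conditions | State before study drug | Conflict: worsening needs a grade from before the drug |
| 5.1.2, DLT window | Opens post dose, Cycle 1 Day 1 | Conflict: the labelled baseline lies inside the window |
| 9.4.2, treatment-emergent by worst grade | Not defined | Undetermined |
| 9.7, pre-dose events | First dose, equated with study Day 1 | Ambiguous on Day 1 itself |

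On the last row, a symptom that starts on Day 1 before dosing is earlier than the first dose but not earlier than Day 1. It meets one test and fails the other. Section 8.1.1 asks for start and end dates, and a date alone does not order events within Day 1.

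**3. What is known of the pre-dose state from other sources?**

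- Prior-therapy toxicity: checking the 4.2 criterion requires grading it, and 7.1 places the eligibility evaluation before treatment. Apart from alopecia, what can remain is Grade 1.
- Laboratory values: taken at screening, and 9.7 calculates CTCAE grades for those that CTCAE covers.
- Conditions: 9.7 records all active ones in the medical history, and 6.1 includes a review of systems.
- Events after consent: Appendix C, item 1, starts reporting at signed consent.

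Still missing is a required grade for symptoms such as fatigue, diarrhea or pain close to dosing. Screening may be up to 28 days old, and history and review of systems are not required to be graded. The 4.2 limit covers toxicity of earlier therapy or procedures, not symptoms of the cancer itself.

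**4. Can the label change a DLT count?** The definition in 5.1.2 is built on treatment-related toxicity of Grade 3 or higher, plus Grade 2 or higher pneumonitis or interstitial lung disease that does not resolve in the stated time. It makes no reference to a baseline grade. A qualifying event after the Day 1 dose falls within the window whatever the visit record calls it, and a residual Grade 1 effect cannot qualify. No route from the wording of 6.2 to a different 3+3 decision follows from the text.

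**5. Can it change the phase II endpoint?** Disease control at 4 months is based on tumor assessment. It does not use toxicity grades.

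**The case against.** The strongest reply is that adverse event status follows from onset, not from the name of a visit. Section 8.1.1 defines pre-existing by reference to the start of study drug, Appendix C collects events from consent, 9.7 separates events before first dose, and 5.1.2 counts from the first dose. Under all of these a reaction after the infusion is an adverse event. No provision makes the 6.2 assessment the formal reference grade, and the calendar row carries neither the word baseline nor a timing. Eligibility also forces some grading before treatment, and footnote b may put CTCAE noting ahead of the dose.

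Most of this stands, and it rules out three stronger readings that a reader might infer:

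- *That no graded assessment exists before treatment.* The eligibility check and the laboratory data contradict this, and footnote b leaves the order open. The supported statement is that none is explicitly scheduled.
- *That the analysis takes its reference grade on drug.* Only the label in 6.2 suggests this; the analysis text does not.
- *That one misassigned event would move a cohort's DLT count from 0 to 1 or from 1 to 2.* Section 5.1.2 does not support this, for the reasons in step 4.

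The reply does not remove the conflict itself. Staff who follow 6.2 would file as baseline what 5.1.2 and 8.1.1 treat as on-treatment, and section 5.5.8 says infusion reactions usually arise during or soon after the infusion, which is when this check would be made. Onset dates identify symptoms that began earlier, but they supply neither a grade from just before dosing nor the order of events within Day 1.

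**Conclusion.** The point holds as a mis-timed and internally inconsistent step. Section 6.2 places the labelled baseline after dosing, no pre-dose toxicity assessment is explicitly scheduled, and the label conflicts with 8.1.1 and with the start of the DLT window in 5.1.2. The gap in the schedule applies to every treated patient. Its consequence is confined to the treatment-emergent and drug-related adverse event tables, mainly low-grade symptoms and reactions on Day 1.

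The number of events misassigned cannot be estimated, because the documents give no frequency for pre-existing symptoms or Day 1 reactions in this population. The conclusion assumes that sites follow 6.2 as written and do not routinely record symptom grades before the first dose. If footnote b is carried out before dosing, much of the harm disappears and the wording conflict remains. DLT counts, 3+3 decisions, the phase II endpoint and the sample size are not shown to be affected. The correction is worth making because it is cheap and the missing grades cannot be reconstructed.

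**What to change.** - **Section 6.2 and calendar footnote b:** reconcile them by stating that the baseline toxicity assessment, graded by CTCAE v4.03, is completed on Cycle 1 Day 1 before the first dose of either drug.
- **Section 6.2:** list the post-dose check on the same day as a separate adverse event assessment, without the word baseline.
- **Sections 9.4.2 and 9.7:** define treatment-emergent as onset or worsening after the first dose, relative to the last pre-dose grade. Using the first dose as the only boundary also removes the ambiguity over Day 1 in 9.7.
- **Calendar, optional:** mark the toxicity row at screening. This is one way to document the earlier state, but it is not needed once the pre-dose Day 1 assessment is explicit.

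The cost is a few lines of text and one extra pre-dose recording at a visit that already takes place. No visit is added.

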## 6.3 Cycle 2 day 1 and subsequent cycles (max of 32 cycles)

- History and assessment to include brief examination, vital signs (heart rate, respiration rate, temperature and BP) and review of systems
- Toxicity/AE assessment
- ECOG Performance Status Assessment
- Hematology (hemoglobin, HCT, RBC, WBC with differential (neutrophils, bands, lymphocytes, monocytes, eosinophils and basophils) and platelet count
- Chemistry (ALT, AST, AP, total bilirubin, direct bilirubin, LDH, creatine kinase, lipase, amylase glucose, calcium, phosphate, magnesium, bicarbonate, sodium, potassium, chloride, creatinine, BUN, total protein and albumin
- Pregnancy test will be performed at baseline for WOCBP and then only as clinically indicated
- 

## 6.4 Start of every 3rd cycle (Cycle 3, Cycle 6, etc.)

- Radiologic assessment: CT scan or MRI (chest, abdomen, pelvis) with tumor measurement and disease assessment of non-measurable disease according to RECIST 1.1 and irRC criteria (please see Appendix B)
- TSH and free T4
- Carcinoembryonic antigen (CEA)

- [REDACTED]

## 6.5 End of Treatment Visit and Follow up

### *End of Treatment Visit*

The end of treatment visit should be conducted when it is confirmed by the investigator that the patient will receive no further doses of drug on study.

- History and assessment to include brief examination, vital signs (heart rate, respiration rate, temperature and BP) and review of systems
- Toxicity/AE assessment
- ECOG Performance Status Assessment
- Hematology (hemoglobin, HCT, RBC, WBC with differential (neutrophils, bands, lymphocytes, monocytes, eosinophils and basophils) and platelet count
- Chemistry (ALT, AST, AP, total bilirubin, direct bilirubin, LDH, creatine kinase, lipase, amylase glucose, calcium, phosphate, magnesium, bicarbonate, sodium
- Radiologic assessment: CT scan or MRI (chest, abdomen, pelvis) with tumor measurement and disease assessment of non-measurable disease according to RECIST 1.1 and irRC criteria (please see Appendix B) may be conducted if it has not been performed within the last 4 weeks.

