#### **4.3.1 Screen Failures/Dropouts/Replacements**

A subject who discontinues study participation prematurely for any reasons except death, disease progression and severe toxicity is defined as a dropout. A subject who, for any reason (e.g., failure to satisfy the selection criteria), terminates the study before the time point used for the definition of “dropout” (see above) is regarded a “screening failure”. Subjects who withdraw from treatment (for any reason) during dose seeking phase may be replaced. Patients will be

considered inevaluable for the primary endpoint of disease control rate if they do not have at least one post-baseline disease response assessment. Inevaluable patients may be replaced.

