- h. Hepatitis B surface antigen, surface antibody, and Hepatitis C antibody
- i. Pregnancy test will be performed at baseline for WOCBP and then only as clinically indicated
- j. After off treatment following disease progression survival f/u, can be performed over the phone every 3 months
- k. Archival tissues ( 10 unstained slides) if available
- l. The PBMC should be viably frozen (for flow cytometric analysis) and the plasma frozen separately .The actual analyses used will be based on response and determined by the investigator at a later date. Two green top (Sodium Heparin) tubes (about 20 ml) will be used each time. This will ONLY be collected at the screening and at the beginning of the 3rd cycle.
- m. If a subject discontinues treatment due to confirmed PD, only the EOT disease assessment is required if it has been > 4 weeks since the last disease assessment
- n. The safety follow-up visit will be approximately 30 days after the last dose or prior to the start of a subsequent anti-cancer therapy.

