### 9.3 Analysis Sets

All subjects who receive at least one dose of the study medication will be included in the safety evaluation.

All subjects who undergo at least one staging reassessment will be used for efficacy evaluations.

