### **Definitions**

**Evaluable for toxicity.** All patients will be evaluable for toxicity from the time of their first treatment with ibrutinib or pembrolizumab.

**Evaluable for objective response.** Only those patients who have measurable disease present at baseline, have received at least one cycle of therapy, and have had their disease re-evaluated will be considered evaluable for response. These patients will have their response classified according to the definitions stated below. (Note: Patients who exhibit objective disease progression prior to the end of cycle 1 will also be considered evaluable.)

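### The end-of-treatment scan is optional in Section 6.5 but scheduled in the calendar, and for patients who stop before their first on-treatment scan it can settle whether they count in the disease control rate

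*Combined protocol and SAP*

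**What the plan says.** Four places bear on the EOT tumor assessment.

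- **Section 6.5** lists it at the End of Treatment Visit and says it "may be conducted if it has not been performed within the last 4 weeks".
- **The 6.6 calendar** marks the row "Tumor Measurement/Disease Assessment" at screening, at Cycle 3 and every third cycle after that, and at EOT.
- **Footnote m**, attached to the EOT column, opens with patients who stop for confirmed progression and says that "only the EOT disease assessment is required if it has been > 4 weeks since the last disease assessment".
- **Footnote c** says tumor assessment "will be collected at screening, after every 3 cycles, and as clinically indicated". It does not name EOT.

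The consequence of having no scan is set elsewhere. Under 4.3.1, patients are "considered inevaluable for the primary endpoint of disease control rate if they do not have at least one post-baseline disease response assessment", and the section adds: "Inevaluable patients may be replaced". Section 9.3 is consistent with this: "All subjects who undergo at least one staging reassessment will be used for efficacy evaluations". Section 5.6 states that the trial is open-label.

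**The concern.** A site cannot tell from these passages whether a patient who stops early for toxicity, deterioration or personal choice must be scanned. For most patients this does not affect evaluability, because a Cycle 3 scan already makes them evaluable. For a patient who stops before that scan it does. The EOT assessment is then the only scheduled post-baseline scan left, since the calendar shows none at the safety visit or in survival follow-up.

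If the scan is done, the patient is in the denominator. If it is not, the patient is inevaluable and may be replaced. The choice lies with staff who know how the patient is doing. In refractory disease, patients who stop this early are plausibly mostly failures, so each omission tends to raise the observed disease control rate. With a success rule of 4 in 32, a few replaced failures matter.

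**Working it through.** **1. Who is affected.** Cycles last 3 weeks (5.1), and 6.4 places the first on-treatment scan at the start of Cycle 3: 2 × 21 + 1 = day 43. Read literally, footnote c's interval of three cycles would give 3 × 21 + 1 = day 64. The gap concerns patients who stop before that scan without documented progression.

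**2. The plan's own design.** Section 9.2 gives a null rate of 5%, a target of 20%, α = 0.10 and power 0.90. The trial continues with at least 1 of 18 and succeeds with at least 4 of 32. The probability of a positive result at rate p is

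P(p) = Σ (x = 1 to 18) Bin(x; 18, p) × Pr[Bin(14, p) ≥ max(0, 4 − x)].

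At p = 0.05:

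| Stage 1 successes | Probability | Chance of reaching 4 in total | Product |
|---|---|---|---|
| 1 | 0.3763 | 0.0301 | 0.0113 |
| 2 | 0.1683 | 0.1530 | 0.0258 |
| 3 | 0.0473 | 0.5123 | 0.0242 |
| 4 or more | 0.0109 | 1 | 0.0109 |

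The sum is 0.072. At p = 0.20 the same formula gives 0.9015. A search over all two-stage designs meeting these limits returns 18 and 32 with the same cut-offs, so the stated design reproduces.

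**3. Effect of dropping and replacing unscanned patients.** Let x be the share of treated patients with no post-baseline scan. Assume that all of them are failures, that all are replaced, and that the 5% null refers to all treated patients. The rate among those counted is then 0.05/(1 − x).

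| x (assumed) | Rate among counted | Type I error |
|---|---|---|
| 0 | 5.00% | 0.072 |
| 5% | 5.26% | 0.084 |
| 10% | 5.56% | 0.097 |
| 15% | 5.88% | 0.114 |
| 20% | 6.25% | 0.134 |

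The error reaches 0.10 when the counted rate is 5.61%, which is x = 1 − 0.05/0.0561, or about 10.9%.

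**4. Where x comes from.** The documents do not give it. The nearest figure is the synopsis's 10% attrition: (12 + 32)/0.9 = 48.9, hence around 49 recruited. That attrition is not defined as having no scan. Also, x covers every unscanned patient, including those who die or are lost, and not only those missed because 6.5 says *may*.

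**5. What one case looks like.** Suppose 36 patients are treated, 4 have disease control and 4 are unscanned. Dropping the unscanned gives 4/32 = 12.5%, which meets the rule. The all-treated rate is 4/36 = 11.1%.

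**The case against.** The strongest reply is that this is a wording mismatch and the real driver is the evaluability rule. Much of that stands. The table in the working measures the whole rule in 4.3.1 and 9.3, and the part due to *may* is a subset of unknown size. If 5% was meant as a rate among evaluable patients (Section 3 plans 32 evaluable subjects), type I error stays at 0.072.

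Footnote m can also be read two ways. A reader might infer that the scan is compulsory only where progression is already known. But with the calendar's mark at EOT, the footnote can equally be a relaxation: everyone is scanned, except patients with confirmed progression who were scanned recently. The documents do not settle which is meant, so that inference is not supported.

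There are partial safeguards. Footnote c allows clinically indicated scans, so some deteriorating patients will be imaged anyway. Appendix B adds: "Patients who exhibit objective disease progression prior to the end of cycle 1 will also be considered evaluable". That note is written for objective response in measurable disease, whereas eligibility also admits non-measurable disease and 4.3.1 has its own rule for disease control. It therefore does not close the gap.

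Finally, a scan required whatever the reason for stopping would conflict with 4.3, which restricts imaging in pregnancy and exempts patients who withdraw consent for all procedures. The fix has to respect this.

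**Conclusion.** The inconsistency between 6.5 and the calendar is certain. It can affect the primary endpoint, but only for patients who stop before their first on-treatment scan without documented progression. The likely direction favours the drug, on the assumption that these patients are mostly failures.

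The size cannot be fixed from the documents. Under the working's assumptions, a 10% unscanned share uses most of the margin between 0.072 and 0.10 without exceeding it; a breach needs more than about 10.9%.

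A reader might go further and infer that the optional scan governs entry to the primary analysis in general, or that type I error is already above 0.10. Neither is supported: anyone with a Cycle 3 scan is already evaluable, and no figure in the documents puts the unscanned share above the crossing point. The change is still worth making, because it is cheap and removes a discretionary step.

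**What to change.** 1. Reconcile 6.5, the 6.6 calendar and footnotes c and m. The EOT tumor assessment already in the calendar should be expected for every patient who stops without documented progression and has no post-baseline scan in the previous 4 weeks. State that a screening scan does not count towards the 4 weeks: screening imaging may be up to 28 days before first treatment, so it could otherwise excuse a very early stopper. Keep the exceptions in 4.3 for pregnancy and for withdrawal of consent for all procedures.
2. Amend 4.3.1 and 9.3 so that the primary disease control analysis counts all treated phase II patients, with no assessment counted as no disease control. Keep the evaluable set as a sensitivity analysis. This is needed because a required scan cannot recover patients who die or are lost first.
3. State how stable disease on an EOT scan taken well before 4 months is classified for the 4-month endpoint.

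**Cost.** A few early stoppers have a scan that is already scheduled, and the observed rate may be slightly lower. If the 20% target was meant for scanned patients only, counting all 32 treated patients lowers power from 0.90 to 0.876 with 5% unscanned, 0.846 with 10% and 0.768 with 20% (the rule evaluated at 0.20 × (1 − x)). If 20% is an all-treated target, power stays at 0.90. The sponsor should say which was meant. The decision rule need not change.
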